Quality of Life will be assessed through the use of two measures to assess various dimensions of quality of life and be used as our secondary outcome measures surrounding quality of life.

The *Short-Form-12 (SF-12)*¹⁰¹ is a 12-item questionnaire that assesses an individual's perceived health status with higher scores indicating higher perceived physical and mental functioning. Research has found high test-retest reliability and internal consistency¹⁰¹. The total score on the mental health functioning subscale will be used.

The *Quality of Life Inventory (QLI)*¹⁰² is a 16-item self-report questionnaire that assesses life satisfaction across multiple domains in 16 areas (e.g., work, love, family, etc.). Participants are asked to rate items on a 3-point Likert scale indicating importance and satisfaction across each domain. Research has found it has a high level of internal reliability, construct validity, and validation within clinical samples¹⁰³. Total scores range from -6 to +6 because total scores are calculated by averaging satisfaction ratings assigned nonzero importance ratings. The total score on the QLI will be used.

Insomnia will be assessed using the *Insomnia Severity Index (ISI)*¹⁰⁴, which is a widely used 7-item Likert scale that assesses sleep disturbances with items asking about difficulty initiating/maintaining sleep, daytime consequences, anxiety and satisfaction with sleep. It has found to be valid and reliable as a measure of sleep disturbance¹⁰⁵. The ISI total score will be used as one of our secondary measures assessing subjective sleep outcome.

Symptoms of PTSD will be assessed using the *PTSD Checklist – Civilian version (PCL-C)*, which is a 17-item questionnaire that assesses how bothersome participants have found a particular problem/symptom to be in the past month, using a 5-point scale. Research has found it has good psychometric properties.¹²⁷ The PCL-C total score will be used as a secondary outcome measure assessing PTSD symptoms.

Symptoms of Anxiety will be assessed using the *Generalized Anxiety Disorder-7 (GAD-7)*, which is a 7-item self-report scale that assesses the frequency of restlessness, worrying, and other symptoms of anxiety over the past two weeks. The scale has good reliability and construct, criterion, factorial, and procedural validity.¹²⁸ The GAD-7 total score will be used as one of our secondary measures assessing subjective symptoms of anxiety.

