While eligibility criteria require a stable history of depressive medication use or non-use, patients may change (drop, add) medications during the twelve week study period. While randomization should equalize patient characteristics between groups and other research has found it has no effect on the relationship between BA and changes in depressive symptoms^{74, 79}, medication change during the course of the trial will be assessed and if necessary it can be examined as a time-varying variable. If a sufficient number of patients are on two or more medications during the course of this trial, we will assess the association (i.e. linear vs. nominal) between the number of medications and depressive symptoms using the likelihood ratio test. Then, the number of depressive medications (in stacked format) will be entered into our model primarily to adjust the other coefficients (time, time*group) for the potential confounding effect on the rate of change in depressive symptoms between groups, due to medication.

Aim 1 (b): To evaluate the efficacy of a 4-session BA-PC in improving other secondary subjective outcomes compared to TAU. Similar to our primary depression outcome, secondary outcomes (i.e., sleep, quality of life, level of environmental reward from experiences) measured at baseline, week 6, and 12 will be analyzed by forming a MLM.

Aim 1 (c): To evaluate a higher level of treatment engagement. For the number of treatment sessions completed, non-parametric methods, such as Kolmogorov-Smirnov, will be used to examine differences between BA-PC and TAU conditions. For those participants continuing to experience moderate-severe symptoms at week 12, we will use chi-square techniques to examine rates of engagement in specialty care using data collected at 24 weeks.

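### The rating scale, scoring rule and -6 to +6 range stated for the Quality of Life Inventory cannot all be right, so this secondary score needs its codes and formula stated

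*Combined protocol and SAP*

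**What the plan says.** The QLI is described in the combined protocol and SAP under Measures, Week 0: Baseline Assessment, Quality of Life. The paragraph says that it "assesses life satisfaction across multiple domains in 16 areas", and makes three statements that bear on the score:

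- Response scale: "Participants are asked to rate items on a 3-point Likert scale indicating importance and satisfaction across each domain".
- Scoring rule and range, in one sentence: "Total scores range from -6 to +6 because total scores are calculated by averaging satisfaction ratings assigned nonzero importance ratings".
- Variable for analysis: "The total score on the QLI will be used".

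The QLI and the SF-12 are the two quality-of-life instruments, to "be used as our secondary outcome measures surrounding quality of life". Table 1 schedules the QLI at weeks 0, 6, 12 and 24. Under Data Analysis and Statistical Considerations, Aim 1 (b) takes the "secondary outcomes (i.e., sleep, quality of life, level of environmental reward from experiences) measured at baseline, week 6, and 12" into a multilevel model.

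No other section gives numeric codes for the importance or satisfaction ratings, or a scoring formula. The paragraph cites the instrument's manual (reference 102) and a validation study (reference 103).

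**The concern.** The scoring sentence offers the averaging rule as the reason for the range, and the rule cannot be the reason. An average of satisfaction ratings cannot go beyond the satisfaction scale, and a 3-point scale in any usual coding stops well short of 6 in either direction. At least one of the response scale, the rule and the range is misdescribed, and the text does not show which.

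What is at stake is the definition of a secondary outcome. In the rule as written, importance does one thing: it removes areas rated zero. Every area that remains counts equally, whether it matters slightly or greatly to the Veteran. If the intended total weights areas by importance, an analyst who follows the sentence and one who follows the manual would compute different variables, and only one of these could be on the stated scale. Importance is not incidental here, because the intervention description has BA-PC build on activities tied to the Veteran's own values.

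**Working it through.** **Inputs.** From the QLI paragraph: 16 areas; a 3-point scale for importance and satisfaction; total = mean of satisfaction over areas with non-zero importance; stated range -6 to +6, a width of 12. Item codes are not given, so the codings below are assumptions, tried in turn.

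**Step 1: can the stated rule reproduce the stated range?** For any set of ratings, min(rating) ≤ mean ≤ max(rating), however many areas are averaged. The bounds under the written rule, and under an alternative that averages importance × satisfaction products over areas of non-zero importance, are:

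| Satisfaction coding | Mean of satisfaction (as written) | Mean of products, importance 0 to 2 | Mean of products, importance up to 3 |
|---|---|---|---|
| 1 to 3 | 1 to 3 | 1 to 6 | 1 to 9 |
| 0 to 2 | 0 to 2 | 0 to 4 | 0 to 6 |
| -1 to +1 | -1 to +1 | -2 to +2 | -3 to +3 |
| -3, 0, +3 | -3 to +3 | -6 to +6 | -9 to +9 |
| -2 to +2 | -2 to +2 | -4 to +4 | -6 to +6 |
| -3 to +3 | -3 to +3 | -6 to +6 | -9 to +9 |

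The stated range is not reproduced in the second column. A 3-point scale in unit steps has width 2, against 12. The widest conventional coding gives width 6, half of what is stated. The written rule reaches ±6 only if the satisfaction items are themselves coded out to -6 and +6 (for example -6, 0, +6), and nothing in the documents suggests that.

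**Step 2: what would give ±6?** Under the product rule, importance 0 to 2 with satisfaction out to ±3 gives 2 × 3 = 6, and importance up to 3 with satisfaction out to ±2 gives 3 × 2 = 6. With satisfaction coded -1 to +1 the product rule reaches only ±2 or ±3. If satisfaction runs from -3 to +3 in unit steps, it is not a 3-point scale, and the response-scale sentence needs correcting too. If it is coded -3, 0, +3, that sentence survives. The documents do not decide between these.

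**Step 3: do the two rules differ by more than scale?** Assume importance 0 to 2 and satisfaction -3 to +3, over 16 areas.

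- Patient A: 8 areas at +3 with importance 2, and 8 at -3 with importance 1. Unweighted: (8×3 - 8×3)/16 = 0. Weighted: (8×2×3 - 8×1×3)/16 = (48 - 24)/16 = +1.5.
- Patient B: the importances are reversed. Unweighted: 0. Weighted: (24 - 48)/16 = -1.5.
- Now move one of patient B's importance-2 areas from -3 to +3. Unweighted: (9×3 - 7×3)/16 = 6/16 = +0.375, above patient A. Weighted: (8×1×3 + 1×2×3 - 7×2×3)/16 = (24 + 6 - 42)/16 = -0.75, below patient A.

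The order of two patients can therefore reverse, so one score is not a rescaling of the other.

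**Step 4: how far apart are they in general?** With independent, uniform random ratings under the same assumed codes, importance given non-zero is 1 or 2 with equal chance. The correlation of the two scores is then E(I)/√E(I²) = 1.5/√2.5 = 0.95. A simulation gave the same 0.95, with standard deviations of 0.67 (unweighted) and 1.07 (weighted). This illustrates the relation between the rules. It does not predict what this trial's data would show.

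**The case against.** The strongest reply is that this is loose descriptive prose about a published instrument. The operative instruction is "The total score on the QLI will be used", the manual is cited, and a -6 to +6 range points to the instrument's standard total. A team that scores from the manual would never use the faulty clause, and the error would be confined to wording. This stands as a possibility. The documents neither show it nor rule it out, and a written scoring rule that cannot yield its own stated range should be corrected either way.

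Four stronger readings are tempting, and the documents do not support them.

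- A reader might infer that the trial will analyse a different endpoint from the one described. That follows only if the sentence is applied literally, and the plan also points to the manual.
- A reader might infer that multiplication by importance must be the missing step. That is an inference from the range. No multiplication is mentioned, and more than one pair of codes gives ±6.
- A reader might infer that the arm comparison would be invalid. One rule would apply to both randomised arms, so the contrast from the model is a valid comparison of whatever score is used. Only its units would fail to match the quoted range.
- A reader might infer that smaller numbers under the written rule mean a diluted effect. Take two areas under the codes assumed in Step 3: one with importance 2 rising from -1 to +2, the other with importance 1 staying at +1. The unweighted score changes by 1.5 on a width of 6, and the weighted score by 3.0 on a width of 12. Both are 25% of the range, so this shows rescaling alone. The real difference between the rules is the change in ranking shown in Step 3, and a correlation of about 0.95 suggests that it may be modest.

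**Conclusion.** The point holds as an internal contradiction in the definition of one secondary outcome. It rests on the bounds of a mean, and it stands for every conventional coding; only an implausible coding of satisfaction out to ±6 escapes it. Followed literally, the rule would yield a score off the stated scale, at most half as wide under the codings tried, and could order some patients differently from an importance-weighted total. The size of that second effect depends on assumed codes. Which of the three statements is wrong cannot be settled from the documents.

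The consequence is minor. The primary PHQ-9 analysis and the sample size of 144 do not use the QLI.

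**What to change.** In the Quality of Life paragraph of the Measures section:

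1. State the numeric codes for importance and for satisfaction separately, and correct the 3-point description if it does not fit both.
2. Replace the scoring sentence with the exact formula from the cited manual, including how missing items and a record with every importance rated zero are handled. The likely form is importance × satisfaction, averaged over areas of non-zero importance, but this must be verified in the manual before it is written in.
3. Give the range that follows from those codes and that formula.
4. Confirm that the scoring program applies the same rule at weeks 0, 6, 12 and 24.

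The cost is a few sentences and one check of the scoring code. Both ratings are already requested for each area, so no new data are needed.

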The proposed study is a single blind randomized, controlled trial (N=144) with two conditions (4-session BA-PC or TAU) that uses an intent to treat design. Following an initial telephone assessment session, all patients who agree to participate and who meet all inclusion criteria will be asked to participate in the study. As depicted in **Figure 2**, all Veterans will complete a baseline assessment. Eligible Veterans will be randomized in equal proportions to one of two conditions (4-session BA-PC or TAU). All Veterans will complete biweekly brief telephone mood assessments for the first 12 weeks. These brief biweekly assessments can also be completed in-person, if they align with another assessment or if the participant prefers to meet in-person. Comprehensive assessments will occur at 6 weeks and 12 (post-treatment), as well as at 24 weeks. After 12 weeks (post-treatment), all participants will be allowed to seek additional psychological treatment, if desired.

Settings

This study will be implemented in four different primary care clinics in VISN 2 (Syracuse VAMC, Canandaigua, Buffalo VAMC's, and Rochester Outpatient clinic). We will seek Buffalo IRB approval as well.

Study Population

Power analyses revealed that a total of 144 Veterans (72 Veterans per group) will need to be randomized to provide 80% power to detect a medium effect of the intervention on depressive symptoms at the 12-week post-

treatment time point, while accounting for a 30% attrition rate across the 12-weeks. Using the previously collected data to give indication of our screening rates and rates of eligibility and consent to enroll in the trial, we expect to be able to recruit 4-5 eligible patients per month across a 33-month recruitment time period resulting in the ability to recruit approximately 165 Veterans. Ultimately, we would need to conduct telephone screens on approximately 335-379 depending on the specific eligibility (38%-43%) rate used from our preliminary study.

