The initial assessment will primarily occur over the telephone; however, any Veteran requesting to be seen in person can also complete the assessment during an in-person visit. During the initial assessment, patients will complete an informed consent process and then be asked to verbally complete: a) a demographics questionnaire, b) the Personal Health Questionnaire-9 (PHQ-9)³⁹ assessing depressed mood, c) the MINI International Neuropsychiatric Interview modules for current mania and psychosis symptoms commonly used by the BHL to assess these same symptoms, and d) a medication and treatment history questionnaire assessing their history of bipolar disorder, engagement in treatment, and use of antidepressants.

At the end of the screening session, research staff will review the various services available for all Veterans at their local VA. For those patients who are eligible to continue to the second part of the study, staff will also briefly describe the study. Research staff will facilitate a referral to any option chosen. All participants will be thanked for their time and will be sent \$15 for completing this telephone assessment.

Baseline Assessment (Week 0)

Those patients who meet eligibility criteria and are interested in participating in the second part of the study will be scheduled for an in-person baseline assessment. Following informed consent and HIPAA waiver, research staff will confirm eligibility by examining the Veteran's CPRS record to ensure that he/she meets eligibility criteria.

As shown in Table 1, participants will be asked to complete self-report assessments, including those assessing mood, quality of life, SI, insomnia, and environmental reward from activities. Participants will be compensated \$40 for completing the in-person session.

Randomization

Those participants eligible to continue in the study (based on CPRS review) will be called after their baseline appointment by a member of the research team to schedule their next in-person session based on being randomized in equal proportions to one of two interventions (4-session BA-PC or TAU) using a stratified block random assignment based on two factors: 1) "mild to moderate" (PHQ-9 score between 10-15) or "severe" (PHQ-9>15) depression and 2) presence or absence of SI (SSI \geq 1).

Assessments

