Aim 1 (a, d): To evaluate the efficacy of a BA-PC in reducing depressive symptoms compared to TAU.

MLM will be used to test the primary null hypothesis that no differences exist in the rate of change in depressive symptoms measured by the PHQ-9 between BA-PC and TAU against the two-sided alternative that differences do exist. A composite equation consisting of within and between person effects will be used to analyze our data. The within-person (level 1) equation estimates participants' unique intercept (time=0) and outcome trajectory. The between-person (level 2) equation estimates the average initial status (e.g., week 0 PHQ-9 total score) and rate of change in the primary outcome (e.g., PHQ-9 total score). If the alternative hypothesis is confirmed, there would be a significant cross-level interaction between group and time of assessment suggesting a greater rate of improvement across time among participants randomized to BA-PC condition relative to TAU.

Below is the multi-level composite equation that will be utilized to model depressive symptom severity. The true depression score for the i^{th} person at the j^{th} time point is a linear combination of a between-subject main effect for group, a main effect for time, and a cross-level interaction term between group and time allowing for the fixed effect slope estimate to vary between groups. Random effects include an intercept and slope. Both level-1 and 2 (subject) residuals are assumed to be normally distributed.

$$Dep_{ij} = \underbrace{\gamma_{00} + \gamma_{01}Group_i + \gamma_{10}Time_{ij} + \gamma_{11}Group_i * Time_{ij}}_{Fixed} + \underbrace{\mu_{oi} + \mu_{li}Time_{ij}}_{Random} + \varepsilon_{ij}$$

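### The two stratification factors appear in no planned model, so the reported standard error for the primary group-by-time test is slightly too large and the test mildly conservative

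*Combined protocol and SAP*

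**What the plan says.** Under Design Overview, "Eligible Veterans will be randomized in equal proportions to one of two conditions". The Randomization section adds that this is a "stratified block random assignment based on two factors". The first factor sets a "PHQ-9 score between 10-15" against a score above 15; the second is "presence or absence of SI", defined as SSI of at least 1. That makes four cells. Site is not a factor and block size is not stated.

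The analysis section then describes these models:

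- **Initial analyses:** a 2 x 2 repeated measures ANOVA (condition by baseline/week 12).
- **Aim 1 (a, d):** a multilevel model, introduced with "A composite equation consisting of within and between person effects will be used to analyze our data". Fixed effects are group, time and group x time, with a random intercept and slope. Week-0 PHQ-9 enters as the time-0 outcome, not as a covariate. Quadratic and piecewise versions change only the time terms.
- **Aim 1 (b):** secondary outcomes "will be analyzed by forming a MLM", described as similar to the primary model.
- **Aim 3 (a):** suicidal ideation as an exploratory outcome, by MLM or GEE, with no equation.
- **Note on Missing Data:** a pattern-mixture alternative that adds a missingness-pattern variable.

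Neither stratification factor is a covariate in any of them. The only adjustment named is number of antidepressant medications, if needed, and that can change after randomisation.

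**The concern.** Blocking within strata forces the arms to be nearly balanced on severity and suicidal ideation. The treatment estimate therefore varies less from trial to trial than it would under simple randomisation. A model without the strata leaves the between-stratum variation in its error term, so its standard error describes a noisier design than the one used. Confidence intervals come out too wide and the test rejects too seldom.

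At stake is a small amount of reported precision and power, in a trial sized so that "a total of 144 Veterans (72 Veterans per group) will need to be randomized to provide 80% power to detect a medium effect". Validity in the direction that usually causes worry, false positives, is not at stake.

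**Working it through.** **Figure in the plan.** The plan states no standard error to reproduce. Its nearest figure is 144 patients for 80% power. Alpha, the numerical effect size and the repeated-measures correlation are not stated, so 80% is taken as nominal and 144 as given.

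**Inputs from the documents.** N = 144, 1:1 allocation, two binary stratification factors, PHQ-9 of at least 10 at entry, seven PHQ-9 visits from week 0 to week 12, two-sided test, 30% attrition.

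**Inputs assumed.** Alpha 0.05; blocks of 4; true-intercept SD 3.5; residual SD 3-4; slope SD 0.2-0.3 per week; intercept-slope correlation 0 to -0.6; suicidal ideation prevalence 3.5-40%; effect of suicidal ideation on slope 0 or 0.2 per week.

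**Step 1: primary slope test, complete data.** With balanced data the group x time test equals a regression of each patient's least-squares slope on group. Adding strata to that regression is the same as adding strata x time to the multilevel model. Each setting had 2,500 simulated trials under no effect.

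| Setting varied | Planned SE | SE with strata x time | Planned/adjusted | True SD without, with strata | Type I error without, with strata |
|---|---|---|---|---|---|
| Intercept-slope correlation 0 | 0.0680 | 0.0670 | 1.015 | 0.0674, 0.0674 | 5.1%, 5.4% |
| n = 100 | 0.0797 | 0.0765 | 1.042 | 0.0763, 0.0762 | 4.4%, 5.3% |
| Slope SD 0.2, residual SD 4 | 0.0677 | 0.0646 | 1.048 | 0.0639, 0.0637 | 3.4%, 4.6% |
| SI slope effect 0.2, prevalence 20% | 0.0684 | 0.0639 | 1.070 | 0.0638, 0.0636 | 3.7%, 4.8% |
| SI slope effect 0.2, prevalence 40% | 0.0690 | 0.0639 | 1.080 | 0.0630, 0.0630 | 3.6%, 4.8% |
| Intercept-slope correlation -0.6 | 0.0642 | 0.0589 | 1.090 | 0.0585, 0.0584 | 2.9%, 4.5% |

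The planned SE is about 1.5-9% above the adjusted one (0.8-9.8% above the simulated SD, which has a Monte Carlo error of about 1.4%). The true SD hardly moves. As a check, type I error should be 2Φ(-1.96 x SE/SD). At SE/SD = 1.008 this is 4.8%, and at 1.098 it is 3.1%. Both agree with the simulated 5.1% and 2.9% within the Monte Carlo error of 0.4 points.

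**Step 2: power.** Let k be planned SE divided by adjusted SE. Take 80% as the nominal power at the planned SE, so effect/SE = 1.960 + 0.842 = 2.802. Under the stratified design:

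- power as planned = Φ(0.842 x k)
- power with strata x time = Φ(2.802 x k - 1.960)

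| k | As planned | With strata x time |
|---|---|---|
| 1.015 | 80.4% | 81.1% |
| 1.039 | 80.9% | 82.9% |
| 1.09 | 82.1% | 86.3% |

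The gain is roughly 1-4 points. A direct simulation with a true effect gave 88.6% against 89.6%.

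**Step 3: the 2 x 2 ANOVA.** Its condition x time test is a two-sample test on change scores. Over the same settings, strata cut the SE by 2.7% (0.9050 to 0.8809) up to 10.7% (0.8515 to 0.7601). Unadjusted type I error was 2.8-4.2%.

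**Step 4: main effects only, and dropout.** With complete data, stratum main effects do not touch the group x time contrast. A mixed model with 30% dropout (400 runs) gave a mean SE of 0.893 as planned, 0.918 with stratum main effects and 0.890 with strata x time. The last is a cut of 1 - 0.890/0.893 = 0.3%. SE/SD was 1.073 as planned and still 1.068 with strata x time. With 400 runs the SD itself has an error of about 1/√800 = 3.5%, so this run suggests a smaller gain but does not settle it.

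**Step 5: rare suicidal ideation.** The nearest figure in the documents is the Background's 3.5% among patients with depression seen by integrated providers: 0.035 x 144 ≈ 5 patients. At that prevalence the SI factor adds almost nothing.

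**The case against.** The strongest case against acting is that the primary test is a slope test and the severity stratum is a cut of week-0 PHQ-9, which is already the first point of each trajectory. Differences in level are therefore absorbed, and only the link between stratum and slope is left to gain from. Every variance behind the sizes above is assumed, and the one run with dropout shows a gain of 0.3%. All of this stands, and it is why the effect is called modest. It does not remove the omission or change its direction.

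Three stronger readings are tempting, and none is supported:

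- **A reader might infer that precision is thrown away.** It is not: the true SD of the estimate is the same with or without strata. The wide standard error and the lost power are one loss, not two.
- **A reader might infer SE cuts of up to about 13%.** Cuts of that size arise for a week-12 or change score with week-0 PHQ-9 as a continuous covariate. That is another remedy applied to another analysis. It does lower the true SD: at correlation -0.6, adding continuous baseline to the strata took the change-score SD from 0.7651 without adjustment to 0.7155. That gain cannot be credited to the strata or carried over to the slope test.
- **A reader might infer that Aim 3 suffers most.** The plan treats suicidal ideation as exploratory, stresses size of effect over significance and leaves the method open. Prevalence in the trial is not given, and no calculation on SSI or the secondary outcomes supports a size there.

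**Conclusion.** The omission is certain on the documents: two factors steer the randomisation and no planned model contains either. The consequence for the primary group-by-time test is a standard error overstated by roughly 1-9% and a loss of about 1-4 power points, with unadjusted type I error at or below 5% within simulation error. Other assumed variances gave similar sizes, with SE cuts of 2-6% and 4-7%. These figures rest on complete data, blocks of 4 and the assumed inputs listed above; with 30% dropout the gain may be smaller. For the change-score ANOVA the overstatement is about 3-11%. There is no bias and no inflation of false positives, so this is an inexpensive improvement and not a threat to the trial's conclusions.

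**What to change.** Pre-specify both stratification factors, coded as randomised, each with its interaction with the time terms. Do this in the linear, quadratic and piecewise primary models, in the medication-adjusted version and in the secondary-outcome models of Aim 1 (b). Do the same in the Aim 3 model where the prevalence of suicidal ideation allows. Stratum main effects alone are not enough for the slope test.

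In the baseline-to-week-12 change-score analysis, week-0 PHQ-9 as a continuous covariate plus the SI factor may replace the severity stratum.

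The Randomization section places a PHQ-9 score of 15 in the lower stratum, while the description of the PHQ-9 under Measures calls 15 or above severe. The two must be reconciled, and the analysis should state which coding the randomisation actually used.

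The cost is a few sentences of analysis plan. The linear model gains 2 factors x (1 main effect + 1 time interaction) = 4 parameters, and the piecewise model 2 x (1 + 2) = 6. No additional data or patients are needed.
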